5.3.3 Evaluating Adverse Events

An investigator or a designee will evaluate and record adverse events according to the NCI-CTCAE version 5.0 as standard practice per institution guidelines.

Attribution - the determination of whether an adverse event is related to a medical treatment or procedure.

- **Definite** the adverse event is clearly related to the investigational agent(s).
- **Probable** the adverse event is likely related to the investigational agent(s).
- **Possible** the adverse event may be related to the investigational agent(s).
- **Unlikely** The adverse event is doubtfully related to the investigational agent(s).
- Unrelated The adverse event is clearly NOT related to the investigational agent(s).

A review of the safety databases across clinical development programs for grapiprant (ARY007) of MedDRA preferred terms of supraventricular tachycardia at that time (August 2019) revealed a total of 0 events reported in subjects treated to date with grapiprant up to 300 mg BID. A review of all potentially treatment-related cardiac events revealed a total of 9 events: 1 episode of sinus bradycardia; 1 episode of cardiac flutter; 2 episodes of palpitations; 2 episodes of vasodilation; 2 episodes of prolonged QT interval, and 1 episode of ST-T change on ECG. As a result of these findings, blood pressure will continue to be monitored for early phase studies, and patients with a significant cardiac history will be excluded from enrollment.

Events of Clinical Interest

In addition to the events noted previously, one event of thrombosis, deemed by the investigator not to be related to study treatment, was reported as an event of clinical interest. The event was grade 3 and resolved without sequelae.

See the investigator brochure for detail on events of clinical interest defined for grapiprant.

6.2 Eribulin

The most common adverse reactions ($\geq 25\%$) reported in patients receiving eribulin were neutropenia, anemia, asthenia/fatigue, alopecia, peripheral neuropathy, nausea, and constipation. The most common serious adverse reactions reported in patients receiving eribulin were febrile neutropenia (4%) and neutropenia (2%). The most common adverse reaction resulting in discontinuation of eribulin was peripheral neuropathy (5%). The adverse reactions described in Table 2 were identified in 750 patients treated in the previous clinical trial (EMBRACE trial). In the study, patients were randomized (2:1) to receive either eribulin (1.4 mg/m² on days 1 and 8 of a 21-day cycle) or single-agent treatment chosen by their physician (control group). A total of 503 patients received eribulin and 247 patients in the control group received therapy consisting of chemotherapy (total 97%)

Protocol 2021-0077 Proprietary Information of MD Anderson PI: [name]

Co-PI: [name] Date: 11/22/2022

[anthracyclines 10%, capecitabine 18%, gemcitabine 19%, taxanes 15%, vinorelbine 25%, other chemotherapies 10%]) or hormonal therapy (3%). The median duration of exposure was 118 days for patients receiving eribulin and 63 days for patients receiving control therapy. **Table 6** reports the most common adverse reactions occurring in at least 10% of patients in either group.

Adverse reactions

Cytopenias

Grade 3 neutropenia occurred in 28% (143/503) of patients who received eribulin in the EMBRACE trial, and 29% (144/503) of patients experienced grade 4 neutropenia. Febrile neutropenia occurred in 5% (23/503) of patients; two patients (0.4%) died from complications of febrile neutropenia. Dose reduction due to neutropenia was required in 12% (62/503) of patients, and discontinuation was required in <1% of patients. The mean time to nadir was 13 days, and the meantime to recovery from severe neutropenia (<500/mm³) was 8 days. Grade 3 or greater thrombocytopenia occurred in 1% (7/503) of patients. G-CSF (granulocyte colony-stimulating factor) or GM-CSF (granulocyte-macrophage colony-stimulating factor) was used in 19% of patients who received eribulin.

Peripheral Neuropathy

In the EMBRACE trial, 17% of enrolled patients had grade 1 peripheral neuropathy, and 3% of patients had grade 2 peripheral neuropathy at baseline. Dose reduction due to peripheral neuropathy was required by 3% (14/503) of patients who received eribulin. Four percent (20/503) of patients experienced peripheral motor neuropathy of any grade, and 2% (8/503) of patients developed grade 3 peripheral motor neuropathy.

Liver Function Test Abnormalities

Among patients with grade 0 or 1 ALT levels at baseline, 18% of eribulin-treated patients experienced grade 2 or greater ALT elevation. One eribulin-treated patient without documented liver metastases had concomitant grade 2 elevations in bilirubin and ALT; these abnormalities resolved and did not recur with re-exposure to eribulin.

Less Common Adverse Reactions

The following additional adverse reactions were reported in \geq 5% to \leq 10% of the eribulin-treated group:

- Eye disorders: increased lacrimation
- Gastrointestinal disorders: dyspepsia, abdominal pain, stomatitis, dry mouth
- General disorders and administration site conditions: peripheral edema
- Infections and infestations: upper respiratory tract infection
- Metabolism and nutrition disorders: hypokalemia
- Musculoskeletal and connective tissue disorders: muscle spasms, muscular weakness
- Nervous system disorders: dysgeusia, dizziness
- Psychiatric disorders: insomnia, depression
- Skin and subcutaneous tissue disorders: rash

Product: Grapiprant
Protocol 2021-0077 Proprietary Information of MD Anderson
Pi: [name]

PI: [name] Co-PI: [name] Date: 11/22/2022

Table 6. Adverse reactions with a per-patient incidence of at least 10% in the study

Adverse Reactions		AVEN 503	Control Group n=247		
	All Grades	≥ Grade 3	All Grades	≥ Grade 3	
Blood and lymphatic system disorders ^b	•			•	
Neutropenia	82%	57%	53%	23%	
Anemia	58%	2%	55%	4%	
Nervous system disorders	•	•			
Peripheral neuropathy ^c	35%	8%	16%	2%	
Headache	19%	<1%	12%	<1%	
General disorders	•	•	•	-	
Asthenia/Fatigue	54%	10%	40%	11%	
Pyrexia	21%	<1%	13%	<1%	
Mucosal inflammation	9%	1%	10%	2%	
Gastrointestinal disorders	-		•	-	
Nausea	35%	1%	28%	3%	
Constipation	25%	1%	21%	1%	
Vomiting	18%	1%	18%	1%	
Diarrhea	18%	0	18%	0	
Musculoskeletal and connective tissue d	isorders				
Arthralgia/Myalgia	22%	<1%	12%	1%	
Back pain	16%	1%	7%	2%	
Bone pain	12%	2%	9%	2%	
Pain in extremity	11%	1%	10%	1%	
Metabolism and nutrition disorders	•			•	
Decreased weight	21%	1%	14%	<1%	
Anorexia	20%	1%	13%	1%	
Respiratory, thoracic, and mediastinal of	disorders				
Dyspnea	16%	4%	13%	4%	
Cough	14%	0	9%	0	
Skin and subcutaneous tissue disorders					
Alopecia	45%	NA ^d	10%	NA ^d	
Infections					
Urinary Tract Infection	10%	1%	5%	0	

^a adverse reactions were graded per National Cancer Institute Criteria for Adverse Events version 4.0.

^b based upon laboratory data.

^c includes peripheral neuropathy, peripheral sensorimotor neuropathy, peripheral motor neuropathy, polyneuropathy, peripheral sensory neuropathy, and paraesthesia.

^d not applicable; (grading system does not specify > Grade 2 for alopecia).

Protocol 2021-0077 Proprietary Information of MD Anderson PI: [name]

Co-PI: [name] Date: 11/22/2022

7.0 STATISTICAL ANALYSIS PLAN

The design of the present study is phase Ib/II. Previous phase I clinical trial conducted in colorectal cancer and non-small cell lung cancer has established P2RD as 300 mg BID when grapiprant was combined with an immune checkpoint inhibitor. DLT was not observed in the group with 300 mg BID, and the most frequent adverse event was the elevation of liver enzymes. We expect that even if grapiprant was combined with eribulin, the combination treatment will be safely administered; however, we will start the combination from the phase Ib part to ensure safety. The decision of deescalation is described in **Figure 2**. The maximum sample size of this study is **25 patients**.

In the phase Ib part, a safety lead-in to the phase II part, the three enrolled patients will initially start grapiprant with 300 mg BID every day and eribulin (1.4 mg/m², day 1 and day 8 of every cycle). We will monitor DLT during the 1st cycle of the treatment. If we observe < 2/3 DLT, we will enroll 3 more patients. If we observe 0 or 1/6 DLT, we will start phase II in that dose and roll over the patients to phase II. If we observe DLT \geq 2/3 or 2/6 patients, we will de-escalate the dosing to 200 mg BID. In de-escalation (200 mg cohort), if we observe < 2/3 DLT, enroll 3 more patients. If we observe 0 or 1/6 DLT, we will start phase II in that dose and roll over the patients to phase II. If we observe DLT \geq 2/3 or 2/6 patients, we will stop the safety trial.

For phase II, the same toxicities that are defined as DLT in phase Ib will be continuously monitored during the first cycle of treatment using the following safety rule: After the first 9 patients (including the first 6 patient rolled over from phase Ib part), if the grade 3/4 toxicity rate >30%, the investigators will inspect the totality of the safety data and potentially terminate the trial for safety.

Phase II adopts the Bayesian optimal phase II (BOP2) design with the null hypothesis H0: CBR = 10% versus the alternative hypothesis H1: CBR = 30%. If the phase II part starts with 300 mg dosing, we will enroll 6 patients and evaluate the clinical benefit in 12 patients (including 6 patients from the phase Ib cohort). For the purpose of futility monitoring, the assessment window for CBR is 24 weeks. If we observed 2 or more clinical benefits in 12 patients, we will proceed to enroll 13 patients and claim the study promising if we observed 5 or more clinical benefits in 25 patients. This design yields the power of 86% with the type I error of 10%.

If the phase II part starts with 200 mg dosing, we will enroll 5 patients and evaluate the clinical benefit in 11 patients (including 6 patients from the phase Ib cohort). If we observed 2 or more clinical benefits in 11 patients, we will proceed to stage 2. For stage 2, (a) if 3 patients treated at 300mg, we will enroll additional 11 patients, and we claim the study promising if we observed 4 or more clinical benefit in 22 (or 19) patients; and (b) if 6 patients treated at 300mg, we will enroll additional 8 patients and we claim the study promising if we observed 4 or more clinical benefit in 19 patients. The power of the design is 86% and 82%, respectively in case (a) and (b), given the type I error of 10%. The operating characteristics for the phase II portion of the trial are summarized in the **Table 7** below:

Table 7: The Operating Characteristics for Phase II

Scenario	Clinical Benefit Rate	Early Stopping (%)	Claim Promising (%)	Average Number of Patients (%)
1	0.1	65.9	8.3	16.4
2	0.2	27.5	52.0	21.4
3	0.3	8.5	86.4	23.9

Co-PI: [name] Date: 11/22/2022

[figure not shown]
Scenario	Clinical Benefit Rate	Early Stopping (%)	Claim Promising (%)	Average Number of Patients (%)
4	0.4	2.0	97.5	24.7
5	0.5	0.3	99.7	25.0

Product: Grapiprant Protocol 2021-0077 Proprietary Information of MD Anderson PI: [name]

Co-PI: [name]

Date: 11/22/2022

Figure 2. Trial design for phase Ib/II of grapiprant and eribulin treatment

Co-PI: [name] Date: 11/22/2022

The CBR and ORR will be summarized by frequency and percentage with 95% exact confidence intervals for all patients and by doses. Time to progression (TTP), progression-free survival (PFS), and overall survival (OS) will be summarized using the Kaplan-Meier method, including median with 95% confidence intervals.

For each exploratory outcome measure (see 6.2, Biomarker Assessments), samples will be acquired pre- and post-treatment. Change associated with treatment will be assessed by t-test and regression models with relation to treatment time, with adjustment for relevant demographic and baseline covariates. A logistic regression model will be used to assess the association between objective response status and change in exploratory outcomes. A proportional hazard model will be used to assess the association between TTP, PFS, and OS with the change in urine prostaglandin E2 metabolite. Additional statistical methods may be used.

The Investigator is responsible for completing an efficacy/safety summary report and submitting it to the IND Office Medical Affairs and Safety Group, for review and approval.

Phase1b:

After the first 3 evaluable patients complete 1 cycle of study treatment, and every 3 patients thereafter. IND Office approval must be obtained, prior to expanding/changing dose levels.

Phase II:

Toxicity summary will be submitted after the first 9 evaluable patients (including the 6 patients treated at MTD), then every 6 evaluable patients complete 1 cycle of treatment.

Efficacy summary:

If the MTD is 300mg, summary will be submitted after 12 evaluable patients (including the 6 patients treated at MTD), complete 24 weeks of treatment and after the 25 evaluable patients complete 24 weeks cycles of treatment.

If the MTD is 200 mg, Summary will be submitted after 11 evaluable patients (including the 6 patients treated at MTD), complete 24 weeks of treatment, and after 25 evaluable patients complete 24 cycles of treatment.

A copy of the safety summary report should be placed in the Investigator's Regulatory Binder under "sponsor correspondence".

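### In the 200 mg branch entered after 3 patients at 300 mg (case (a)), the rule of 4 or more of 22 has an exact type I error of 13.2%, not the stated 10%

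*Combined protocol and SAP*

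**What the plan says.** All of this is in Section 7.0, Statistical Analysis Plan. Phase II tests the "null hypothesis H0: CBR = 10% versus the alternative hypothesis H1: CBR = 30" percent, where CBR is the clinical benefit rate, a primary outcome in Section 4.1.

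If 2 or more of the first 3 patients, or 2 of 6, have a dose-limiting toxicity (DLT) at 300 mg, "we will de-escalate the dosing to 200 mg BID". The 200 mg efficacy rule then runs as follows:

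- Stage 1 counts 6 phase Ib patients plus 5 new ones: "If we observed 2 or more clinical benefits in 11 patients, we will proceed to stage 2".
- Case (a), stage 2: "a) if 3 patients treated at 300mg, we will enroll additional 11 patients", and then "we claim the study promising if we observed 4 or more clinical benefit in 22 (or 19) patients".
- Case (b) applies when 6 patients were treated at 300 mg. It adds 8 patients and needs 4 or more benefits in 19.

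The operating characteristics claimed are: "The power of the design is 86% and 82%, respectively in case (a) and (b), given the type I error of 10" percent. Table 7 gives operating characteristics only for the 300 mg design (2 or more of 12, then 5 or more of 25).

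**The concern.** Cases (a) and (b) share the same first stage and the same final cutoff of 4, but case (a) looks at three more patients. With the cutoff fixed, each added patient raises the chance of reaching it under the null hypothesis. If case (b) already sits near 10%, case (a) must be above it, yet one 10% figure is given for both. Table 7 does not cover either case, so a reader cannot see this from the plan. Case (a) also names two final denominators.

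At stake is the go decision on the primary efficacy outcome in this branch. It would be reported as controlled at 10% when it is not. If the denominator or cutoff were settled after data are in, that choice would be post hoc.

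**Working it through.** **Inputs (Section 7.0).** Null CBR 0.10, alternative 0.30. 300 mg design: n1 = 12, continue at 2 or more, n = 25, claim at 5 or more. Case (a): n1 = 11, continue at 2 or more, n = 22, claim at 4 or more. Case (b): the same with n = 19. Futility is treated as binding (Section 4.8 says of the 12-patient look that the study will stop; the same is assumed for the 11-patient look), and all patients are taken as evaluable.

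**Formula.** With r1 the stage 1 cutoff, r the final cutoff and n2 = n − n1, P(claim | p) is the sum over x ≥ r1 of P(Bin(n1, p) = x) × P(Bin(n2, p) ≥ r − x). At p = 0.10 this is the type I error; at p = 0.30 it is the power.

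**Reproducing the plan first (300 mg).**

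| CBR | Early stop, computed / Table 7 | Claim promising, computed / Table 7 |
|---|---|---|
| 0.1 | 65.9 / 65.9% | 8.33 / 8.3% |
| 0.2 | 27.5 / 27.5% | 52.04 / 52.0% |
| 0.3 | 8.5 / 8.5% | 86.35 / 86.4% |
| 0.4 | 2.0 / 2.0% | 97.46 / 97.5% |
| 0.5 | 0.3 / 0.3% | 99.65 / 99.7% |

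The method is therefore the plan's own. Since 8.3% is described there as 10%, the 10% is a ceiling.

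**Case (a), 4 or more of 22.**

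| Stage 1 benefits | Type I error (p = 0.10) | Power (p = 0.30) |
|---|---|---|
| 2 of 11, then 2 or more of 11 | 0.21308 × 0.30264 = 0.06449 | 0.19975 × 0.88701 = 0.17718 |
| 3 of 11, then 1 or more of 11 | 0.07103 × 0.68619 = 0.04874 | 0.25682 × 0.98023 = 0.25174 |
| 4 or more of 11 | 0.01853 | 0.43044 |
| Total | **0.13176** | **0.85936** |

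**Case (b), 4 or more of 19.** Type I error: 0.03982 + 0.04045 + 0.01853 = 0.0988. Power: 0.14875 + 0.24202 + 0.43044 = 0.8212. Both agree with the plan.

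**Does another reading rescue case (a)?** After 2 or more of 11:

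| Final rule | Type I error | Power |
|---|---|---|
| 4 of 19 | 9.9% | 82.1% |
| 4 of 20 | 11.0% | 83.8% |
| 4 of 21 | 12.1% | 85.0% |
| 4 of 22 | 13.2% | 85.9% |
| 5 of 22 | 5.4% | 79.1% |

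So 19 is the largest total that keeps the error within 10% at a cutoff of 4. Over interim cutoffs 0 to 4 and final cutoffs 3 to 6 at 11 and 22 patients, no pair gives error of 10% or less with 86% power. The highest power within the limit that keeps a futility stop is 1 of 11 then 5 of 22 (6.1%, 83.1%). Ignoring the futility stop makes case (a) worse, at 17.2%.

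**Reach.** The branch is entered with probability P(2 or more DLTs of 3 at 300 mg) × P(0 or 1 of 6 at 200 mg, following the 3 + 3 path). The documents give no DLT rate for the combination, so the rates below are assumptions. The trial-wide rate weights 8.33%, 13.18% and 9.88% by the chance of ending in each design.

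| DLT rate, 300 / 200 mg | Case (a) entered | Trial-wide false claim |
|---|---|---|
| 10 / 10% | 2.5% | 8.5% |
| 20 / 20% | 6.8% | 7.9% |
| 30 / 30% | 9.1% | 6.2% |
| 40 / 20% | 23.1% | 7.7% |
| 50 / 10% | 44.3% | 10.2% |

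**The case against.** The strongest reply is about weight. This is one wrong figure in one contingency of a 25-patient single-arm study whose main design checks out. Under the assumed DLT rates, replacing 13.18% with a true 10% would change the trial-wide false-claim probability by only 0.08, 0.22, 0.29, 0.73 and 1.41 points. The one trial-wide figure above 10% needs a fall in DLT rate from 50% to 10% between the doses, for which the documents give no basis. That stands: overall error control is not lost.

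It can also be said that the 19 in case (a) is a leftover from case (b), since 11 + 11 = 22 and the 86% power both point to 22. That is probably right, but it confirms the error: at 22 the 10% is false.

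Third, the agreement found for the 300 mg design and case (b) covers their stated error and power only, with binding futility and full evaluability. If the stop were not enforced, the errors would be 9.8% (300 mg) and 11.5% (case (b)). Section 4.9.2 also excludes unevaluable patients without replacing them, so realised denominators may be smaller. These are fair limits. Neither brings case (a), with 22 evaluable patients, to 10%.

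**Conclusion.** The concern holds. In case (a) the rule of 2 or more of 11, then 4 or more of 22, has an exact type I error of 13.2% against the stated 10%, with power of 85.9% against the stated 86%. No choice between the two denominators in the text delivers both stated figures. The 300 mg design and case (b) reproduce theirs.

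The result assumes binding futility and that all planned patients are evaluable. Figure 2 is not shown in the text reviewed and was not checked. The consequence is limited to the branch reached by 2 or more DLTs in the first 3 patients at 300 mg and then 0 or 1 of 6 at 200 mg. Within it, a primary-endpoint decision rule carries a false error rate, which should be corrected before the branch is used.

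A minor related point is the 200 mg efficacy-summary line in Section 7.0, "after 25 evaluable patients complete 24 cycles of treatment". With 21-day cycles that is 24 × 21 = 504 days, or 72 weeks, while the CBR window is 24 weeks. The 25 is not impossible (3 + 22 and 6 + 19 both equal 25), and the SAP does plan an all-patient summary ("The CBR and ORR will be summarized by frequency and percentage with 95% exact confidence intervals for all patients and by doses"). The line does not say whether it means that set or the 22 or 19 patients on whom the 200 mg decision rests.

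**What to change.** In Section 7.0, correct case (a) in one of three ways and give it a single denominator:

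1. Keep 4 or more of 22, state a type I error of 13.2% and power of 85.9%, and delete the alternative 19.
2. Keep 22 patients, require 5 or more, state 5.4% and 79.1%, and delete the alternative 19.
3. End stage 2 at 19 patients with 4 or more, and state 9.9% and 82.1%. Stage 2 then adds 8 patients rather than 11.

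The trade-off is for the investigators to choose. Option 1 is a change of wording only, with no effect on conduct. Options 2 and 3 change the decision rule, so Figure 2 should be checked against them. None needs extra patients; each makes one stated figure less favourable. It would help to say that the 11-patient futility stop is binding, and to add the 200 mg designs to Table 7.

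In the 200 mg efficacy-summary line, replace cycles with weeks if the CBR window is meant, and say which patients make up the 25.
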